#### **4.5.2. Additional Safety Assessments**

Additional adverse events grouped by MedDRA coded SOC (unless further specificity is listed below or required) with  $\geq 5\%$  occurrence in participants treated with erenumab-aooe will be supplemented with tables of the below evaluations.

##### **4.5.2.1. Clinical Laboratory Evaluation**

- The investigator must review the laboratory report, document this review, and record any clinically relevant changes occurring during the study in the AE section of the CRF. The laboratory reports must be filed with the source documents. Clinically significant abnormal laboratory findings are those which are not associated with the underlying disease, unless judged by the investigator to be more severe than expected for the participant's condition.

This document, including any source code, is the property of [Clinvest Research LLC](#), and may contain proprietary, confidential, or legally privileged information. No part of this report, or any information contained therein, may be disseminated without the written consent of [Clinvest Research LLC](#).

- All laboratory tests with values considered clinically significantly abnormal during participation in the study should be repeated until the values return to normal or baseline or are no longer considered clinically significant by the investigator or medical monitor.
- If such values do not return to normal/baseline within a period of time judged reasonable by the investigator, the etiology should be identified and Clinvest and the medical monitor notified.
- If laboratory values from non-protocol specified laboratory assessments performed at the institution's local laboratory require a change in participant management or are considered clinically significant by the investigator (e.g., SAE or AE or dose modification), then the results must be recorded in the CRF.

#### 4.5.2.2. Electrocardiograms (ECG)

- Single 12-lead ECG will be obtained as outlined in the SoA (see Section 1.2.1). The heart rate, PR, QRS, QT, and QTc intervals will be measured/calculated. Investigators will read final ECG's and determine any abnormalities. The overall interpretation and determination of the clinical relevance of ECG findings will be the responsibility of the investigator.
- AE table will be supplemented if  $\geq 5\%$  of participants treated with erenumab-aooe have AEs reported due to an abnormal ECG finding that have a MedDRA coded SOC of *Cardiac disorders* or *ECG investigations*.

#### 4.5.2.3. Physical and Neurological Examination Findings

- A complete physical examination will include, at a minimum, assessments of the Cardiovascular, Respiratory, and Gastrointestinal systems.
- Height and weight will also be measured and recorded.
- A complete neurological examination will be performed.
- Investigators should pay special attention to clinical signs related to previous serious illnesses.
- AE table will be supplemented if  $\geq 5\%$  of participants treated with erenumab-aooe have AEs reported that have a MedDRA coded PT of *Weight increased* or *Weight decreased*.
- AE tables will be supplemented if  $\geq 5\%$  of participants treated with erenumab-aooe have reported AEs MedDRA coded as:
  - HLTG = *Neurological disorders not elsewhere classified (NEC)*
  - SOC = *Cardiac disorders*
  - SOC = *Respiratory, thoracic and mediastinal disorders*
  - SOC = *Gastrointestinal disorders*

This document, including any source code, is the property of [Clinvest Research LLC](#), and may contain proprietary, confidential, or legally privileged information. No part of this report, or any information contained therein, may be disseminated without the written consent of [Clinvest Research LLC](#).

#### 4.5.2.4. Suicidal Ideation

Participants being treated with erenumab-aooe should be monitored appropriately and observed closely for suicidal ideation and behavior or any other unusual changes in behavior, especially at the beginning and end of the course of intervention, or at the time of dose changes, either increases or decreases. Consideration should be given to discontinuing the study medication in participants who experience signs of suicidal ideation or behavior, following a risk assessment.

Baseline assessment of suicidal ideation and behavior/ intervention emergent suicidal ideation and behavior will be monitored during the study using PHQ-9.

AE table will be supplemented if  $\geq 5\%$  of participants treated with erenumab-aooe have AEs reported that have a MedDRA coded HLGT of *Suicidal and self-injurious behaviours NEC*.

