
 • Self-Efficacy 	
 • General Self-Efficacy Short Form (GSE-SF) scores

 • Severity of worry 	
 • Brief Measure of Worry Severity (BMWS) scores
Exploratory	
To evaluate the efficacy of erenumab on activity and sleep.	Change from baseline to each 4-week treatment month within subjects treated with erenumab-aooe on activity and sleep measured through a wearable device.
To evaluate the efficacy of erenumab on functional impact of migraine.	Change from baseline to each 4-week treatment month within subjects treated with erenumab-aooe on Functional Assessment of Migraine Scale (FAMS) scores.
To evaluate the correlation between the Functional Assessment of Migraine Scale (FAMS) and other migraine related Patient Reported Outcome (PRO) measures.	
Correlation between Functional Assessment of Migraine Scale (FAMS) and the following migraine related Patient Reported Outcome (PRO) measures:
 
 • Global Migraine Functional Impact Questionnaire (MFIQ) • Migraine interictal burden scale (MIBS-4) • Work Productivity and Activity Impairment- Migraine (WPAI-M) • Neuro-QoL Sleep Disturbance Short Form (SDSF) • General Self-Efficacy Short Form (GSE-SF)

This document, including any source code, is the property of [Clinvest Research LLC](#), and may contain proprietary, confidential, or legally privileged information. No part of this report, or any information contained therein, may be disseminated without the written consent of [Clinvest Research LLC](#).

Objectives	Endpoints
	
 • Brief Measure of Worry Severity (BMWS)
Safety	
To evaluate the safety and tolerability of subjects treated with erenumab-aooe.	Safety and tolerability of erenumab-aooe in study participants via collection of adverse events and safety evaluations.

Overall Design:

This is a single group, multicenter, open-label study with a study population of patients who meet International Classification of Headache Disorders 3rd edition (ICHD-III) criteria for migraine with or without aura and have 4 to 20 migraine days per month.

Disclosure Statement:

This is a single-group supportive care study with one arm and no masking.

Number of Participants:

A maximum of 54 participants will be enrolled to study intervention.

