15. clinically relevant or significant ECG abnormalities as determined by the investigator, including ECG with QT interval corrected for heart rate (QTc) using Fridericia's correction formula (QTcF) > 500 msec;
16. history of any of the following cardiovascular conditions:
 - a. Moderate to severe congestive heart failure (New York Heart Association class III or IV);
 - b. Recent (within past 12 months) cerebrovascular accident, myocardial infarction, coronary stenting;
 - c. Uncontrolled hypertension as defined by a confirmed systolic blood pressure > 160 mmHg or diastolic blood pressure > 100 mmHg.
17. active HIV or Hepatitis C infection;
18. allergy to latex;
19. score of > 0 on question 9 on Patient Health Questionnaire (PHQ-9) at any visit;
20. have any other condition, that in the judgment of the investigator, would make the participant unsuitable for inclusion, or would interfere with the participant participating in or completing the study.

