8.2.5. Suicidal Ideation and Behavior Risk Monitoring

Participants being treated with erenumab-aooe should be monitored appropriately and observed closely for suicidal ideation and behavior or any other unusual changes in behavior, especially at the beginning and end of the course of intervention, or at the time of dose changes, either increases or decreases. Consideration should be given to discontinuing the study medication in participants who experience signs of suicidal ideation or behavior, following a risk assessment.

Baseline assessment of suicidal ideation and behavior/ intervention emergent suicidal ideation and behavior will be monitored during the study using PHQ-9.

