### 3. Analysis Sets

Participant Analysis Set	Description
Full	

• All participants enrolled and with at least one administration of IP, will be included in this analysis set. The Full Analysis set will be used to analyze the efficacy and safety endpoints.

This document, including any source code, is the property of [Clinvest Research LLC](#), and may contain proprietary, confidential, or legally privileged information. No part of this report, or any information contained therein, may be disseminated without the written consent of [Clinvest Research LLC](#).

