#### **4.5.1.1. Adverse Events of Special Interest**

Based on the known warnings and precautions identified in AIMOVIG (erenumab) prescribing information, summary tables will be created for the below adverse events of special interest reported by all participants regardless of frequency.

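### Suicidality gets a focused table only from three of 54 participants upward, and no PHQ-9 output is specified although PHQ-9 is the stated monitoring tool

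*SAP*

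**What the plan says.** Protocol 8.2.5 says that baseline and "intervention emergent suicidal ideation and behavior will be monitored during the study using PHQ-9". SAP 4.5.2.4 repeats this: "suicidal ideation and behavior will be monitored during the study using PHQ-9". The schedule of activities has PHQ-9 at Visits 1 to 5 and at Early Discontinuation. Exclusion criterion 19 (Protocol 5.2) is a "score of > 0 on question 9 on Patient Health Questionnaire (PHQ-9) at any visit".

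The only reporting rule in SAP 4.5.2.4 is that the AE table is supplemented if at least 5% "of participants treated with erenumab-aooe have AEs reported that have a MedDRA coded HLGT of" *Suicidal and self-injurious behaviours NEC*. The lead-in at SAP 4.5.2 sets the same condition for all the additional assessments: AEs with at least 5% "occurrence in participants treated with erenumab-aooe will be supplemented with tables of the below evaluations".

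A different rule applies to injection site reactions, constipation and hypertension. For these, SAP 4.5.1.1 says "summary tables will be created for the below adverse events of special interest reported by all participants regardless of frequency". Suicidality is not on that list.

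Two general statements also apply. SAP 4.5 undertakes to summarise all safety endpoints as appropriate, and Protocol 9.4.5 says the same of all AEs. SAP 4.6 plans no other analyses.

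**The concern.** Suicidality has its own monitoring section, a named instrument and an instruction to observe participants closely. Its reporting rule is nevertheless the one used for changes in weight or body temperature: no supplement below 5%. In a trial of this size, that leaves the most likely non-zero results, one or two participants, without a focused display.

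The instrument is a separate matter. The safety endpoint covers safety evaluations as well as AEs, and PHQ-9 is one of those evaluations, but the SAP defines no item 9 count, listing or change. AE coding closes the gap only in part. Under the AE definition (Protocol 10.3.1, SAP 6.4.1), an abnormal safety assessment counts as an AE if the investigator considers it clinically significant. No passage says that a positive item 9 must be recorded as one.

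At stake is how complete and visible the safety report is on a serious topic that the trial set out to monitor. The efficacy analyses are unaffected.

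**Working it through.** **Inputs from the documents**

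- Number treated: "A maximum of 54 participants will be enrolled to study intervention" (Protocol 1.1).
- Denominator: "The Full Analysis set will be used to analyze the efficacy and safety endpoints" (SAP 3), meaning all enrolled participants with at least one administration.
- Trigger: at least 5% (SAP 4.5.2 and 4.5.2.4).

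**Reproducing the plan's 54.** For a paired t-test with d = 0.50, two-sided alpha 0.05 (Protocol 9.4.1) and target power 0.95, the noncentral t distribution gives power 0.9465 at n = 53 and 0.9502 at n = 54. The stated 54 is confirmed.

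**Trigger in participants.** The trigger is the smallest k with k/54 ≥ 0.05. Since 0.05 × 54 = 2.7, k = 3.

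- 1/54 = 1.85%: no supplement
- 2/54 = 3.70%: no supplement
- 3/54 = 5.56%: supplement

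This does not depend on reaching exactly 54. Two cases stay below 5% for any N of 41 or more (2/41 = 4.88%). At N = 40 they reach it (2/40 = 5.0%).

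**Chance of one or two cases.** The documents give no suicidality rate, so p below is an assumption, shown over a range. Participants are taken as independent with the same risk, N = 54:

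P(1 or 2) = 54·p·(1−p)^53 + 1431·p²·(1−p)^52, where 1431 = 54 × 53 / 2.

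At p = 0.02 this is 0.370 + 0.200 = 0.570.

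| Assumed p | At least one case | One or two cases, no supplement | Three or more, supplement |
|---|---|---|---|
| 1% | 0.419 | 0.402 | 0.017 |
| 2% | 0.664 | 0.570 | 0.094 |
| 3% | 0.807 | 0.587 | 0.220 |
| 5% | 0.937 | 0.427 | 0.511 |

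Rows may differ from exact sums by rounding.

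**Where each result would be reported**

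- *One or two participants with an AE in the group.* The general AE tables should include them. SAP 4.5.1 leaves the MedDRA level of the final tables open, so they may be visible only at a higher level. No supplement is produced.
- *Three or more participants.* The general tables plus the supplement. SAP 4.5.2 could be read as then giving a table of the evaluation itself, but it names no PHQ-9 display.
- *Item 9 above 0, recorded as an AE.* As above, according to how it is coded.
- *Item 9 above 0, not recorded as an AE.* No output is specified. Only the general sentence in SAP 4.5 could cover it.

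**Interpretability of item 9.** PHQ-9 and eligibility are both checked at Visit 2, when the first injection is given, and Protocol 5 permits no waivers. If the criterion is applied as written, everyone treated starts with item 9 equal to 0. A later score above 0 is then new since baseline, though not necessarily due to treatment.

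**The case against.** The strongest reply is that the 5% rule governs a supplement and not whether events are reported. Base AE reporting has no threshold, and one or two events in a single-arm trial of at most 54 people are easy to find. A reader might infer that one or two suicidality AEs would go unreported; the documents do not support that. What remains is that the level of the AE tables is open and no focused display is promised.

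A reader might also infer that PHQ-9 results will never be summarised. That too goes beyond the text, because the general commitment in SAP 4.5 could be read to include them. The supportable statement is that no PHQ-9 summary is specified.

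Third, a positive item 9 can become an AE. SAP 4.5.1 includes AEs that staff identify during safety assessment procedures, and events meeting seriousness criteria go to the sponsor within 24 hours whatever their frequency (Protocol 8.3.1). This stands and narrows the gap to positive answers that the investigator does not record as AEs.

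Fourth, the SAP gives a reason for its two tiers: the unconditional tables follow the warnings and precautions in the prescribing information. The documents do not say that the 5% cut-off was meant for common events only. Moving suicidality to the first tier is therefore partly a judgement, but an easy one when the plan names a dedicated tool for it.

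Finally, a PHQ-9 total-score table would describe depression, which is not a study objective. That is accepted, so such a table is not needed to repair this point.

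**Conclusion.** The point holds as a defect in safety reporting. Suicidality AEs get a focused table only from three participants upward, and the named monitoring tool has no specified output. The three-participant trigger is exact for 54 and follows from the documents alone.

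The probabilities of about 40%, 57% and 43% for one or two cases without a supplementary table rest on assumed risks of 1%, 2% and 5%. They illustrate how the rule behaves and are not a forecast for this population, which excludes item 9 above 0 at entry. They concern the supplementary table only, not whether events are reported at all. No estimate or test is affected, and nothing here bears on how a participant with a positive answer is managed.

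**What to change.** In SAP 4.5.2.4:

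1. Remove the 5% condition and list every event in the HLGT *Suicidal and self-injurious behaviours NEC* regardless of frequency, as SAP 4.5.1.1 already does for the adverse events of special interest.
2. Add a by-visit count or listing, including Early Discontinuation, of participants with PHQ-9 item 9 above 0 after Visit 2, whether or not an AE was recorded.

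A summary of the PHQ-9 total score is optional.

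The cost is SAP wording plus one short listing and one small table, all from data already collected. No visit, assessment or clinical rule changes.

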#### 4.5.2.5. Vital Signs

The following vital signs will be collected during the study:

- Blood pressure and pulse measurements.
- Blood pressure and pulse measurements should be preceded by at least 5 minutes of rest for the participant in a quiet setting without distractions (e.g., television, cell phones).
- Vital signs will be measured in a semi-supine position after 5 minutes rest and will include temperature, systolic and diastolic blood pressure, and pulse.
- AE tables will be supplemented if  $\geq 5\%$  of participants treated with erenumab-aooe experience potentially significant vital sign change AEs including those outlined below:
  - AEs that have a MedDRA coded PT of:
    - *Blood pressure systolic decreased*
    - *Blood pressure systolic increased*
    - *Blood pressure diastolic decreased*
    - *Blood pressure diastolic increased*
  - AEs that have a MedDRA coded PT of *Heart rate decreased* or *Heart rate increased*.
  - AEs that have a MedDRA coded PT of *Body temperature decreased* or *Body temperature increased*

### 4.6. Other Analyses

Not Applicable, i.e., there are no other planned analysis for this study.

### 4.7. Interim Analysis

Not Applicable, i.e., there is not a planned interim analysis for this study.

#### **4.8. Changes to Protocol-planned Analyses**

Not Applicable, i.e., there are no changes to the protocol-planned analysis for this study.

This document, including any source code, is the property of [Clinvest Research LLC](#), and may contain proprietary, confidential, or legally privileged information. No part of this report, or any information contained therein, may be disseminated without the written consent of [Clinvest Research LLC](#).

## 5. Sample Size Determination

A meta-analysis of commonly used patient reported outcome (PRO) effect sizes was conducted to determine the expected effect size for the primary endpoint. The meta-analysis revealed participants on erenumab 140mg had an average change score on commonly used PROs with an effect size of  $d = 0.87$ . Additionally, prior research on the MFIQ showed an average correlation of  $r = 0.59$  between the global MFIQ scores and these regularly utilized PROs. Due to the differences in study design between this study and prior studies, the novelty of the MFIQ and the uncertainty of its effect size, and to correct for potential replication errors, we lowered the expected effect size to a more moderate effect size of  $d = 0.50$ .

To determine the needed sample size for this study we utilized G\*Power Version 3.1.9.3 to conduct a power analysis for the primary endpoint analysis comparing baseline global MFIQ scores to the final 4-week treatment period's global MFIQ scores utilizing a within group, repeated measures  $t$ -test. We utilized the conservative effect size of  $d = 0.50$ , alpha set at 0.05, and a power of .95. With these parameters the power analysis indicated a total of 54 participants would need to be analyzed to detect this effect with .95 power.

## 6. Supporting Documentation

### 6.1. Appendix 1: List of Abbreviations

Abbreviation or Term	Definition/Explanation
AE	Adverse Event
ANOVA	Analysis of variance
BMWS	Brief Measure of Worry Severity
CMP	Comprehensive metabolic panel
CRF	Case report form
DHD	Daily headache diary
ECG	Electrocardiography
EF	Emotional Function
FAMS	Functional Assessment of Migraine Scale
FAMS-R	Functional Assessment of Migraine Scale- Research
FAMS-RS	Functional Assessment of Migraine Scale- Research Supplement
GSE-SF	General Self-Efficacy Short Form
ICH	International Council for Harmonisation of Technical Requirements for Pharmaceuticals for Human Use
ICHD-III	International Classification of Headache Disorders 3rd edition
IEC	Independent Ethics Committee(s)
IP	Investigational Product
LOCF	Last observation carried forward
MedDRA	Medical Dictionary for Regulatory Activities
MFIQ	Migraine Functional Impact Questionnaire

This document, including any source code, is the property of [Clinvest Research LLC](#), and may contain proprietary, confidential, or legally privileged information. No part of this report, or any information contained therein, may be disseminated without the written consent of [Clinvest Research LLC](#).

Abbreviation or Term	Definition/Explanation
MIBS-4	Migraine Interictal Burden Scale
PF	Physical Function
PHQ-9	9-Item Depression Patient Health Questionnaire
PRO	Patient reported outcome
SAE	Serious Adverse Event
SAP	Statistical analysis plan
SDSF	Neuro-QoL Sleep Disturbance Short Form
SF	Social Function
SoA	Schedule of Activities
UA	Usual Activities
WOCB	Women of Childbearing Potential
WPAI-M	Work Productivity and Activity Impairment- Migraine

This document, including any source code, is the property of [Clinvest Research LLC](#), and may contain proprietary, confidential, or legally privileged information. No part of this report, or any information contained therein, may be disseminated without the written consent of [Clinvest Research LLC](#).

## 6.2. Appendix 2: International Classification of Headache Disorders, 3rd edition: Migraine with and without aura

### 6.2.1. Migraine without aura

**Description:** Recurrent headache disorder manifesting in attacks lasting 4–72 hours. Typical characteristics of the headache are unilateral location, pulsating quality, moderate or severe intensity, aggravation by routine physical activity and association with nausea and/or photophobia and phonophobia.

#### Diagnostic criteria:

- A. At least five attacks fulfilling criteria B–D
- B. Headache attacks lasting 4–72 hours (when untreated or unsuccessfully treated)
- C. Headache has at least two of the following four characteristics:
  - 1. unilateral location
  - 2. pulsating quality
  - 3. moderate or severe pain intensity
  - 4. aggravation by or causing avoidance of routine physical activity (e.g. walking or climbing stairs)
- D. During headache at least one of the following:
  - 1. nausea and/or vomiting
  - 2. photophobia and phonophobia
- E. Not better accounted for by another ICHD-3 diagnosis.

## 6.2.2. Migraine with aura

**Description:** Recurrent attacks, lasting minutes, of unilateral fully reversible visual, sensory or other central nervous system symptoms that usually develop gradually and are usually followed by headache and associated migraine symptoms.

### Diagnostic criteria:

- A. At least two attacks fulfilling criteria B and C
- B. One or more of the following fully reversible aura symptoms:
  - 1. visual
  - 2. sensory
  - 3. speech and/or language
  - 4. motor
  - 5. brainstem
  - 6. retinal
- C. At least three of the following six characteristics:
  - 1. at least one aura symptom spreads gradually over  $\geq 5$  minutes
  - 2. two or more aura symptoms occur in succession
  - 3. each individual aura symptom lasts 5–60 minutes
  - 4. at least one aura symptom is unilateral
  - 5. at least one aura symptom is positive
  - 6. the aura is accompanied, or followed within 60 minutes, by headache
- D. Not better accounted for by another ICHD-3 diagnosis.

